10.3.4. Reporting of SAEs and AESIs

Table 18: SAE/AESI Reporting to the Sponsor or Designee via an Electronic Data Collection Tool

SAE/AESI Reporting to the Sponsor or Designee via an Electronic Data Collection Tool

- The primary mechanism for reporting an SAE/AESI to the sponsor or designee will be the electronic data collection tool.
- The site will enter the SAE/AESI data as soon as it becomes available within 24 hours of awareness.
- If the electronic data collection tool is unavailable, then the site will use the paper SAE/AESI form (see next section).
- After the trial is completed at a given site, the electronic data collection tool will be taken off-line to
 prevent the entry of new data or changes to existing data.
- If a site receives a report of a new SAE/AESI from a trial participant or receives updated data on a
 previously reported SAE/AESI after the electronic data collection tool has been taken off-line, then the
 site can report this information on the paper SAE/AESI form (see next section) or to the sponsor or
 designee by telephone.

Table 19: SAE/AESI Reporting to the Sponsor or Designee via Paper Form (if needed)

SAE/AESI Reporting to the Sponsor or Designee via Paper Form

- If the electronic data collection tool is unavailable, then the site will use the paper SAE/AESI form. The SAE or AESI paper form should be used to electronically transmit this information to the sponsor or designee.
- Contacts for electronic transmission of the paper SAE/AESI form are provided in the Operations Manual.
- In rare circumstances and in the absence of facsimile equipment, notification by telephone is acceptable
 with a copy of the SAE or AESI data collection tool sent by overnight mail or courier service.
- Initial notification via telephone does not replace the need for the investigator to complete and sign the appropriate SAE or AESI form within the designated reporting time frames.

10.4. Appendix 4: Contraceptive Guidance and Collection of Pregnancy Information

10.4.1. Definitions

10.4.1.1. Highly Effective Form of Contraception (Failure Rate <1%)

A highly effective form of contraception (failure rate of <1%) is defined as follows:

- Combined (estrogen and progestogen containing) hormonal contraception associated with inhibition of ovulation:
 - Oral
 - Intravaginal
 - Transdermal
- Progestogen-only hormonal contraception associated with inhibition of ovulation:
 - Oral
 - Injectable
 - Implantable
- Intrauterine device
- Intrauterine hormone-releasing system
- Bilateral tubal occlusion
- Vasectomized partner
- Sexual abstinence is considered a highly effective method only if defined as refraining from heterosexual intercourse during the entire period of risk associated with the trial treatments. The reliability of sexual abstinence needs to be evaluated in relation to the duration of the clinical trial and the preferred and usual lifestyle of the participant.

10.4.1.2. Acceptable Birth Control Methods (Failure Rate >1% per Year)

Acceptable birth control methods that result in a failure rate of more than 1% per year include the following:

- Progestogen-only oral hormonal contraception, where inhibition of ovulation is not the primary mode of action
- Male or female condom with or without spermicide*
- Cap, diaphragm or sponge with spermicide*

^{*}A combination of male condom with a cap, diaphragm, or sponge with spermicide (double-barrier methods) is also considered acceptable but is not a highly effective birth control method.

10.4.1.3. Contraception and Pregnancy Avoidance Procedures

The following definitions apply for contraception and pregnancy avoidance procedures:

A woman is considered a woman of childbearing potential following menarche and until becoming postmenopausal unless permanently sterile. Permanent sterilization methods include hysterectomy, bilateral oophorectomy, and complete salpingectomy.

In this trial, postmenopausal state is defined as no menses for at least 12 consecutive months without an alternative medical cause in addition to an FSH level >40 IU/mL.

Sterilized male participants should be at least 1 year postbilateral vasectomy and have confirmed that they have obtained documentation of the absence of sperm in the ejaculate or have had bilateral orchidectomy.

10.4.2. Collection of Pregnancy Information

10.4.2.1. Male Participants With Partners Who Become Pregnant

- The investigator will attempt to collect pregnancy information on any male participant's female partner who becomes pregnant while the male participant is in this trial. This applies only to male participants who receive IMP.
- After obtaining the necessary signed informed consent from the pregnant female partner directly, the investigator will record pregnancy information on the appropriate form and submit it to the sponsor within 24 hours of learning of the partner's pregnancy. The female partner will also be followed to determine the outcome of the pregnancy. Information on the status of the mother and child will be forwarded to the sponsor. Generally, the follow-up will be no longer than 12 weeks following the estimated delivery date. Any termination of the pregnancy will be reported regardless of fetal status (presence or absence of anomalies) or indication for the procedure.

10.5. Appendix 5: Future Biospecimen Research

Use/Analysis of Deoxyribonucleic Acid

- Genetic variation may impact a participant's response to trial treatment, susceptibility
 to, and severity and progression of disease. Variable response to trial treatment may
 be due to genetic determinants that impact drug absorption, distribution, metabolism,
 and excretion; mechanism of action of the drug; disease etiology; and/or molecular
 subtype of the disease being treated.
- DNA samples will be used for research related to CVL-354 or major depressive
 disorder and related diseases. They may also be used to develop tests/assays including
 diagnostic tests related to CVL-354 and/or interventions of this drug class and major
 depressive disorder. Genetic research may consist of the analysis of one or more
 candidate genes or the analysis of genetic markers throughout the genome or analysis
 of the entire genome (as appropriate).
- There are no planned analyses of DNA samples. Analyses may be conducted if it is hypothesized that this may help further understand the clinical data.
- The samples may be analyzed as part of a multi-trial assessment of genetic factors involved in the response to CVL-354 or IMPs of this class to understand trial disease or related conditions.
- The results of genetic analyses may be reported in the CSR or in a separate trial summary.
- The sponsor will store the DNA samples in a secure storage space with adequate measures to protect confidentiality.
- The samples will be retained while research on CVL-354 or trial treatments of this class or major depressive disorder continues but no longer than 15 years or other period as per local requirements.

10.6. Appendix 6: Kidney Safety for First-in-Human Trial

10.6.1. Elevations in Serum Creatinine

Serum creatinine (SCr) level may be affected by age, muscle mass, diet, activity, and tubular transporter activity, and SCr elevations can occur without impacting overall kidney function. Nonetheless, kidney function is closely monitored using blood urea nitrogen (BUN), serum creatinine, and urinalysis.

Table 20: Monitoring of Abnormal Kidney Function Tests

Lab Result	Action
Serum creatinine > ULN	Repeat for confirmation approximately 1 hour after drinking a large glass (~250 mL) of water
Urinalysis (UA) • ≥+1 protein • + glucose	Repeat for confirmation approximately 1 hour after drinking a large glass (~250 mL) of water
Active urine sediments (eg, hematuria, pyuria, casts [WBC, RBC, tubular epithelial, or granular])	

Abbreviations: RBC=red blood cell; ULN=upper limit of normal; WBC=white blood cell.

Contact the medical monitor if the repeat confirmation SCr >1.2× ULN or urine continues to have proteinuria, glucosuria, or active urine sediments.

10.6.2. Potential Cases of Acute Kidney Injury

Abnormal values in SCr that meet the KDIGO 2012 (KDIGO, 2012) criteria below, in the absence of other causes of kidney injury, are considered potential cases of acute kidney injury (AKI) and should be regarded as important medical events.

- Increase in SCr ≥0.3 mg/dL (26.5 mmol/L) within 48 hours
- Increase in SCr ≥50% from baseline
- Urine volume output <0.5 mL/kg/h for 6 hours

The baseline is defined as the most recent SCr prior to randomization/dosing.

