	Scree	ening				Follow-up										
Trial Periods/Phases	Screeninga	Check-in ^a				In Cli	Contact ^b									
Day	-30 to -2	-1	1	2	3	4	5	6	7	8-9	10	11-13	14	15/16	17/ET	29
Entrance and History	'			ı		•				•		•			ı	
Informed consent	X															
Assign screening number	X															
Inclusion/exclusion criteria	X	X														
Medical and psychiatric history ^c	←		-													
Demography	X															
History of drug and alcohol use	X															
Test for alcohold	X	X														
Randomization			X													

Safety Assessments																
Height (Screening only) and weight	X	X													X	
Physical/neurological examination ^f	X	X							X						X	
Continuous ECG (Holter)			Xg										Xg			
Standard 12-lead ECGh	X	X	X			X			X		X		X		X	
Supine heart rate and blood pressurei	X	X	X	X	X	X	X	X	X	X	X	X	X	X	X	
Standing heart rate and blood pressure	X	X	X			X			X				X			
Respiratory rate and temperature	X	X	Xk	X^k	X ^k	Xk	Xk	X ^k	X ^k	X ^k	Xk	X ^k	X ^k	X	X	
C-SSRS ¹	X	X		X					X				X		X	
Prior/concomitant treatments ^m	←															-

	Screening		Treatment (In Clinic)											Follow-up		
Trial Periods/Phases	Screeninga	Check-in ^a											In Clinic		Contactb	
Day	-30 to -2	-1	1	2	3	4	5	6	7	8-9	10	11-13	14	15/16	17/ET	29
Adverse event monitoring ⁿ			←												-	
Laboratory																
Blood for safety laboratory	X	X				X			X		X		X		X	
Urine for safety laboratory	X	X				X			X		X		X		X	
Urine drug screeningo	X	X														
Hepatitis B, C, HIV	X															
FSHP	X															
Serum Cystatin-C ^q	X	X				X			X		X		X		X	
Urine β-2-microglobulin ^{q,r}		X											X			
PK blood samples			X	X	X		X		X	X		X	X	X	X	
Urine sample for PK and metabolite scouting		X ^u											Xu			
Blood sample for future biospecimen research ^v		X														
Other																-
Dosing			X	X	X	X	X	X	X	X	X	X	X			
Meals ^w		X	X	X	X	X	X	X	X	X	X	X	X	X	X	
Telephone contact																Xb

Abbreviations: COVID-19=coronavirus disease-2019; C-SSRS=Columbia-Suicide Severity Rating Scale;

-5; ECG=electrocardiogram;

ET=early termination; FSH=follicle stimulating-hormone; IMP=investigational medicinal product; PK=pharmacokinetic; QD=once daily;

Confidential Page 32 of 96 Version 3.0: 25 May 2022

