- j On dosing days, orthostatic blood pressure and heart rate measurements will be obtained at 2 hours after the morning dose with the participants in the standing position.
- ^k Respiratory rate and body temperature will be taken at predose on Days 1 through 14.
- ¹ The "Baseline/Screening" C-SSRS form will be completed for all participants at Screening to determine eligibility. The "Since Last Visit" C-SSRS form will be completed at Check-in to ensure that the participant continues to qualify for the trial and will also be completed on Days 2, 7, 14, and 17/ET.
- m Concomitant medications should be recorded from Screening through the participant's last visit/contact.
- ⁿ Adverse events (serious and nonserious) should be recorded from first dose of IMP through the participant's last visit/contact.
- Additional urine drug screening can be conducted at any time during the trial at the discretion of the investigator.
- ^p A confirmatory FSH is required for all post-menopausal women.
- ^q Laboratory test not part of eligibility.
- The participant should empty their bladder and then drink ~250 mL water. The participant's urine should be collected ~1 hour later.
- s PK samples (1 sample and 1 backup sample) will be obtained predose (within 15 minutes prior to dosing) and 0.5, 1, 2, 3, 4, 6, 8, 12, 16, and 24 hours following administration of the first dose of IMP on Day 1 and on Day 14 at predose (within 15 minutes prior to dosing) and 0.5, 1, 2, 3, 4, 6, 8, 12, 16, 24, 36, 48, and 72 hours after the morning dose. A single predose PK sample will be taken on Days 3, 5, 7, 9, and 11.
- ^u Spot urine samples will be collected on Day -1. Cumulative urine samples will be collected on Day 14 (0-24 hour collection).
- ^v Future biospecimen research sample is optional and is only to be collected if signed consent is obtained from the participant. Sample can be collected at any time prior to initiation of first dose.

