8.3.5. Clinical Safety Laboratory Assessments

See Section 10.2 (Appendix 2) for the list of clinical laboratory tests to be performed and the Schedule of Assessments (Section 1.3) for the timing and frequency.

The investigator must review the laboratory report, document this review, and record any clinically relevant changes occurring during the trial in the AE section of the eCRF. The laboratory reports must be filed with the source documents.

All laboratory tests with values considered clinically significantly abnormal during participation in the trial should be repeated until the values return to normal or baseline or are no longer considered clinically significant by the investigator or medical monitor.

If such values do not return to normal/baseline within a period of time judged reasonable by the investigator, the etiology should be identified and the medical monitor notified.

All protocol-required laboratory assessments, as defined in Section 10.2 (Appendix 2), must be conducted in accordance with the laboratory manual and the Schedule of Assessments.

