10.6.2.1. Marked Elevations in Serum Creatinine

For increases of SCr >50% relative to the participant baseline:

- Temporarily withhold IMP until a repeat SCr as soon as practically feasible, preferably within 24 hours of awareness.
- If the second measurement of SCr is still ≥50% from the participant baseline, IMP should be permanently discontinued.
- Adequate, immediate, supportive measures should be taken if AKI is suspected.

Version 3.0: 25 May 2022

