10.6.2.2. Evaluation of Potential Cases of AKI

Participants suspected of having potential AKI should promptly (as soon as practically feasible, preferably within 24 hours of awareness) have an evaluation, which includes a detailed medical history, physical examination, and laboratory tests.

Laboratory tests include, at a minimum:

- Serum:
 - BUN, creatinine, sodium, potassium, chloride, bicarbonate, phosphorus, and calcium
 - Creatine kinase and cystatin-C
- Urine: Dipstick, microscopic examination, indices, and β-2-microglobulin.

Consider consultation with a nephrologist.

Close daily observation of the participant and assessment of kidney function should be continued until the SCr elevations and the associated abnormal UA results return to baseline or normalize.

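### In Part B, scheduled creatinine draws are 72 to 96 hours apart, so the 48-hour AKI criterion cannot be met on them, and a rise of 0.3 mg/dL or more that is below +50% and not above ULN has no required individual repeat

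*Protocol*

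**What the plan says.** Protocol Section 10.6.2 names three signs of potential AKI, in the absence of another cause: "Increase in SCr ≥0.3 mg/dL (26.5 mmol/L) within 48 hours"; a rise of at least 50% from baseline, with no time window; and urine output below 0.5 mL/kg/h for 6 hours. Baseline is the last creatinine before randomization or dosing. Cases meeting these criteria are to be treated as important medical events.

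In Part B, the row "Blood for safety laboratory" (protocol Section 1.3, Table 3; SAP Appendix 9.1, Table 6) is marked at Screening and on Days -1, 4, 7, 10, 14 and 17/ET. Serum cystatin-C is drawn on the same days. The only timed urine is one 0-24 hour collection on Day 14, with total volume recorded (Section 8.6.2).

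Two rules require a repeat creatinine for an individual:
- Table 20 (Section 10.6.1), for "Serum creatinine > ULN". The next step is "Contact the medical monitor if the repeat confirmation SCr >1.2× ULN".
- Section 10.6.2.1, "For increases of SCr >50% relative to the participant baseline", which also withholds study drug.

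Two further rules depend on judgment. Section 8.3.5 says "All laboratory tests with values considered clinically significantly abnormal during participation in the trial should be repeated". Section 10.6.2.2 begins "Participants suspected of having potential AKI should promptly" and leads to an evaluation that includes creatinine and cystatin-C.

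Section 10.6.2.4 stops escalation if at least two participants at a dose level lose 25% or more of cystatin-C eGFR.

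**The concern.** A criterion with a 48-hour window needs two samples no more than 48 hours apart. Part A has them, at 24 and 48 hours after each dose. Part B, the only repeat-dose part, does not, although cystatin-C and β-2-microglobulin were added there to evaluate renal function after multiple doses.

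The mandatory repeats do not fill the gap. At any baseline above 0.6 mg/dL, a rise of 0.3 mg/dL comes before a rise of 50%. If the value also stays at or below ULN, no rule obliges anyone to confirm it. At stake is whether a rise that Section 10.6.2 would call a potential case, had it been sampled within 48 hours, is confirmed by rule or only if someone judges it worth repeating.

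**Working it through.** **Sampling intervals.** There is no Day 0 (SAP Section 4.1.2.4, Study Day), so Day -1 to Day 4 is 4 days.
- Day -1 to 4: 4 × 24 = 96 h
- Day 4 to 7: 72 h
- Day 7 to 10: 72 h
- Day 10 to 14: 96 h
- Day 14 to 17: 72 h

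None of the 5 intervals is 48 h or less. Clock time does not rescue this: draws three calendar days apart are more than 48 h apart even from late one day to early on the other. Only an early-termination draw could fall closer.

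**Urine criterion.** Output of 0.5 mL/kg/h over 24 h is 12 mL/kg. If all four 6-hour blocks reached 3 mL/kg, the total would be at least 12. A Day 14 total below 12 mL/kg therefore proves at least one breach. A total of 12 or more does not rule one out, and other days have no timed collection.

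**The uncovered band.** For baseline b, it runs from b + 0.3 up to ULN or to just below 1.5b, whichever is lower. As a share of the band from b + 0.3 to 1.5b, at assumed ULN 1.1 / 1.2 / 1.3 / 1.4 mg/dL:
- b = 0.7: 100% at all four
- b = 0.8: 0 / 100 / 100 / 100%
- b = 0.9: 0 / 0 / 67 / 100%, for example (1.30 − 1.20)/(1.35 − 1.20) = 67%
- b = 1.0: 0 / 0 / 0 / 50%
- b = 1.1: 0% at all four

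Example: 0.80 on Days -1 and 4, then 1.15 on Day 7. The rise is 0.35 (44%) over 72 h. A repeat is required at ULN 1.1 but not at 1.2, 1.3 or 1.4.

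**Above ULN.** Table 20 does require a repeat, but it is compared with a value taken after the rise, so it shows a 48-hour rise only if creatinine climbs a further 0.3. For a value below 1.5b, the 1.2 × ULN contact step can be reached only if 1.5b > 1.2 × ULN, that is b > 0.8 × ULN (0.88, 0.96, 1.04 and 1.12 for the four ULNs).

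**Chance of a required repeat.** The model has a true baseline of 0.8, a sustained true level of 1.15, normal proportional error, one shared baseline reading and four later draws (Days 7, 10, 14, 17). The current rule fires if any draw exceeds ULN or 1.5 × baseline. The fix adds any draw at least 0.3 above baseline. Simulated results for CV 5% to 7.5%:
- ULN 1.2: about 72-83% now, about 96-98% with the fix
- ULN 1.3: about 55-65% now, about 95-98% with the fix
- ULN 1.1: over 99% now

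Hand check at ULN 1.1, CV 5%: SD = 1.15 × 0.05 = 0.0575 and z = (1.10 − 1.15)/0.0575 = −0.87. Each draw exceeds ULN with probability 0.81, and over four draws 1 − 0.19⁴ is about 0.999.

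For a rise from 0.9 to 1.25 at ULN 1.3, the current figure is 67-81%. At CV 10%, the current figures are 88% (0.8 to 1.15, ULN 1.2) and 86% (0.9 to 1.25, ULN 1.3). Much of this apparent coverage comes from error pushing a reading over a line that the true value does not cross.

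**False alarms from the fix.** Expected first alarms per cohort = P(Z > 0.3/(b × CV × √2)) × 10 participants × 5 post-baseline samples.
- b = 0.9: 0.00006, 0.042 and 0.46 at CV 5%, 7.5% and 10%
- b = 1.1: 0.003, 0.25 and 1.3

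For b = 1.1 at CV 10%: 0.3/0.1556 = 1.93, P = 0.027, and 0.027 × 50 is about 1.3.

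**The case against.** The best case for the plan is that Section 10.6.2 classifies cases from any data, including unscheduled draws, and nowhere promises that each criterion can be seen on schedule. Participants are domiciled to Day 17, every laboratory report is reviewed, extra tests may be added at any time, and evaluation needs only suspicion. Cystatin-C, which is not affected by the creatinine transporters, is drawn alongside every safety creatinine. Safety urine is taken on the same days, and Table 20 requires repeats for protein or glucose whatever the creatinine. Another scheduled creatinine follows any Day 4 to 14 value within 72 to 96 hours.

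All of this stands, and it rules out some stronger readings:
- A reader might infer that two of the three AKI criteria cannot be met on the Part B schedule. That is not so: the Day 14 urine total can prove a breach, though only in part.
- A reader might infer that every rise up to and including 50% escapes. A rise of exactly 50% is already a potential case under Section 10.6.2, and anything above ULN must be repeated.
- A reader might infer that Part B lacks renal monitoring. Cystatin-C and its stopping rule show otherwise.

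What none of these provides is a required repeat for the individual inside the band. Sections 8.3.5, 10.2 and 10.6.2.2 depend on judgment, and Section 10.6.2.4 needs two participants and governs escalation only.

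It is also fair to say that the fix does not make the 48-hour criterion observable. It adds a broader trigger without a time window, and the amendment should say so.

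**Conclusion.** The point holds as a mismatch between a stated safety criterion and the Part B schedule. The 48-hour rise cannot be met on scheduled samples, and rises of at least 0.3 mg/dL that are below +50% and not above ULN have no mandatory individual repeat. The interval arithmetic needs no assumption.

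The size does rest on assumptions, since the documents give no baseline distribution, ULN or CV. Under the assumed values the gap is material at low baselines or a high ULN and almost absent at a ULN of 1.1. Exclusion criterion 11 (eGFR below 90 at Screening) removes higher baselines, which leaves those where the ULN trigger covers least. The chances above count only repeats that a creatinine rule requires; they give no credit to cystatin-C, urinalysis or investigator action, so they are not chances of missing an injury. No endpoint or planned analysis changes. This is a worthwhile, cheap improvement and not a flaw that undermines the trial.

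**What to change.** Amend Appendix 6 for Part B:
1. Creatinine at least 0.3 mg/dL above the Day -1 baseline at any scheduled sample, whatever the ULN, requires a repeat creatinine with cystatin-C, preferably within 24 hours, read with the cystatin-C already drawn that day.
2. If the rise is confirmed, carry out the Section 10.6.2.2 evaluation and contact the medical monitor.
3. State that this trigger has no time window, that it is a screening trigger and not the KDIGO 48-hour criterion, and that it does not by itself make the case an important medical event or pause dosing. Without this, a confirmed rise could be read as serious under Section 10.3.2 and lead to the dosing pause in Section 4.4.
4. Leave the 50% withhold, discontinue and cohort-stop rules (10.6.2.1, 10.6.2.3) as they are.
5. Note that the 6-hour urine criterion is only partly visible on schedule, through a Day 14 total below 12 mL/kg.

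The same amendment can correct the unit in the criterion: 0.3 mg/dL × 88.4 = 26.5 µmol/L, not mmol/L.

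Cost: no new scheduled samples, no added participants and no required dose interruption, so the trigger itself does not disturb Day 14 steady-state PK. Expect about 0 to 1.3 noise-driven alarms per cohort of 10 at CV 5% to 10%, some of which would already need a repeat under the existing rules. If CVL-354 inhibits creatinine transporters, more participants would have confirmed rises and need evaluation; the paired cystatin-C helps to tell these apart.
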